7.1 Consent

Written consent must be obtained prior to any study-specific procedures being performed, including any study specific screening procedures prior to randomisation. The consent process should be clearly documented in the patient's medical notes and it must be clear that the trial was adequately explained and the patient was able to give informed consent.

To ensure effective communication, in the presence of a language barrier, interpreters will be made available through the hospital translation service. A translator should be available for each patient visit and this should be clearly documented in the patient notes. If a translator is not available the patient should not be recruited to the trial.

Written consent will be taken by a clinician, who has signed / dated the staff authorisation / delegation log.

7.2 Muscle Biopsy:

Muscle biopsies will be performed on all subjects participating in the trial. These are scheduled to take place at visits 3 and 5. It is a day case procedure that is performed by trained personnel using aseptic techniques and under local anaesthesia. Patients will be instructed to observe the surgical site for signs of infection or bleeding, but no biopsy- specific follow-up visits are normally necessary.

The obtained muscle specimens will be transferred to the labs where muscle fibre size and number will be studied along with fat content, anabolic and catabolic pathways. Analysis of the aforementioned will be done through a combination of methodologies, immunohistochemistry, qRT-PCR and Western Blot.

Obtaining a muscle specimen for histopathologic study is an important component of this trial. It provides evidence of muscle changes as a consequence of treatment at the tissue level, for example hypertrophy or hyperplasia of muscle fibres, activation of anabolic pathways and down-regulation of catabolic pathways.

7.3Imaging assessments

7.3.2 Accelerated MRI and MRS

The Newcastle Magnetic Resonance Centre has developed advanced methodology for measuring tissue energetics (31P MRS) and metabolism (1H MRS) as well as conventional images to measure structure and muscle fat infiltration. MRS is a companion technique to the more familiar magnetic resonance imaging (MRI) scan. It is non-invasive and capable of measuring a broad range of biological compounds across a variety of tissues. In other words, it allows us to study muscle metabolism, which is a point of interest in this trial.

In this trial, the total skeletal muscle volume in the upper and lower leg, covering both legs will be measured using a custom fat-water decomposition MRI, accelerated by compressed sensing methods^{XXXIII}. A custom 3-point Dixon sequence will be used to automatically segment the signals from skeletal muscle, bone and subcutaneous fat. The muscle volume of the upper leg will be delimited from the superior aspect of the greater trochanter to the superior aspect of the patella. The muscle volume of the lower leg will be defined from the superior aspect of the talus to the tibial plateau. This method, developed at Newcastle, is not only faster than conventional T1 weighted imaging but can also be analysed more rapidly. These images will also be used to determine the fat fraction of the upper and lower leg muscle compartments, by measuring the percentage of voxels in which fat predominates (>50% of the voxel) for the same defined anatomic region. To assess muscle inflammation, we will measure the T2 relaxation time by multi-echo spin- echo imaging at mid-lower and mid-upper leg, defined with respect to the bony landmarks above.

We will use PRESS single voxel spectroscopy to examine the relative concentration of creatine to water in the soleus at each time point (voxel size approx. 40 mm x 40 mm x 20 mm)^{xxxiv}. We will use ISIS single voxel spectroscopy to examine the concentration of phosphocreatine, ATP and inorganic phosphate in the soleus.

All MRI assessments will be made at the Newcastle MR Centre on a 3T Philips Achieva dStream Scanner using a 28 channel array coil and a 14cm surface coil for 31P MRS. Measurements obtained at base line will be compared to those taken 1 and 6 months later.

There is a small possibility that an unexpected abnormality could be observed of which the patient and their doctors are unaware. The MRI scans will be reviewed by a radiologist in the Newcastle upon Tyne Hospitals NHS Foundation Trust to look for any such findings. The Principal Investigator will be informed of any abnormal findings and will contact the patient's clinical care team or GP to make recommendations about any further investigations which it may be appropriate for them to arrange. Text agreed with the Sponsor to this effect is contained in the Participant Information Sheet.

8 Risks and Benefits of the Proposed Interventions

We will study rheumatoid arthritis patients who have been prescribed Tofacitinib (5mg bd) by their clinical team, in accordance with its license and NICE criteria. From this perspective the risks are no more than for standard care. In terms of additional investigations, patients will provide a slightly larger volume of blood during the 6 months of observation than they would in standard care, but the difference is modest and should not be associated with significant risk. Magnetic resonance imaging and spectroscopy are safe, non-invasive procedures that do not use ionising radiation; DEXA scans involve exposure to a very low dose of radiation. Muscle function testing involves simple tasks (e.g. rising from a chair without using hands) that are not associated with significant risk. Biopsies will be performed by trained personnel under aseptic techniques to ensure the lowest risk of infection. The majority of patients have no adverse reaction to the procedure and it is generally very well tolerated. Possible complications are significant bleeding or bruising (risk of 1 in 100) and nerve damage resulting in localised paraesthesia (risk of 1 in 1000).

The proposed research has the potential to contribute work of significant improvement in our understanding of sarcopenia that is associated with RA. It will have a positive impact on providing targeted future therapy that is beyond joint inflammation albeit having no direct benefits to this study's participants.

9 Statistical Analysis

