2.2 Exploratory objectives

- a. To investigate the relationship between established serum biochemistry muscle tests (listed in section 2.4b) and other serum markers of muscle damage and renal impairment
- b. To investigate potential predictive biomarkers by exploring the relationship between the ex vivo sensitivity of peripheral blood mononuclear cell (PBMC) subset(s) to tofacitinib at baseline with downstream clinical responses to the drug.
- c. To investigate changes in muscle quality through the measurement of the global fat fraction of the upper and lower leg muscle compartments

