2.4 Exploratory endpoint/outcome

- a. Serum cystatin C and myoglobin at baseline, 1 month and 6 months
- b. Percentage change in STAT1/3 phosphorylation of PBMC subset(s) when stimulated with interleukin-6 (IL-6) alone as well as in the presence of tofacitinib – at baseline and at 1 month – and the predictive utility of readout(s) with respect to clinical response to tofacitinib.
- c. Percentage change in fat fraction of upper and lower leg muscle compartments at baseline, 1 month and 6 months. If no difference is observed in this global measure, percentage changes in specific muscle groups (such as quadriceps and hamstrings) may also be measured.

In each case, individual patient data (intra-patient) and pooled group data will be examined, to allow for expected heterogeneity in response.

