2.5 Table of endpoints/outcomes

Objectives	Outcome Measures	Time point(s) of evaluation of this outcome measure (if applicable)
Primary Objective	Primary outcome	
To identify a change in muscle bulk	Compressed sensing (accelerated) MRI	Baseline, 1 month and 6 months

Secondary Objectives		dary outcomes	
a. to identify changes in muscle strength and physical function	a.	Grip strength, timed rise from chair, gait speed	Baseline, 1 month and 6 months
b. muscle biochemistry	b.	Magnetic resonance spectroscopy of skeletal muscle: total creatine to water ratio, content of creatine, phosphocreatine and inorganic phosphate of the soleus	months
c. muscle histology and biochemistry	c.	Muscle Biopsy	Baseline and 6 months
d. To relate changes in serum biochemistry with effects on muscle	d.	Serum creatinine, creatine kinase, aspartate transaminase, LDH	Baseline, 1 month and 6 months
e. To relate changes in muscle to reduction in systemic inflammation	e.	Serum CRP, IL-6, TNF, IFN, IL1, IL17.	Baseline, 1 month and 6 months
f. To seek any overall changes in body composition.	f.	DEXA scan	Baseline, 1 month and 6 months
Exploratory Objective	Explor	atory outcome	
 To investigate the relationship between established serum biochemistry muscle tests (listed in section 2.4b) and other serum markers of muscle damage and renal impairment 	Serum	cystatin C and myoglobin	Baseline, 1 month and 6 months
 b. To investigate potential predictive biomarkers by exploring the relationship between the ex vivo sensitivity of peripheral blood mononuclear cell (PBMC) subset(s) to tofacitinib at 	phosp stimul as wel	ntage change in STAT1/3 horylation of PBMC subset(s) when ated with interleukin-6 (IL-6) alone I as in the presence of tofacitinib, e predictive utility of readout(s)	Baseline and 1 month

	baseline with downstream clinical responses to the drug.	with respect to clinical response to tofacitinib.	
c.	0 0	Percentage change in muscle fat fraction of the upper and lower leg muscle compartments as measured by MRI (analyses of muscle groups may also be performed if no change in global fat fraction is observed)	Baseline, 1 month and 6 months

3 Trial Design

This is an observational, single arm study designed to provide preliminary information on changes in muscle structure, biochemistry and function in patients receiving tofacitinib. Data from this study will be used to power a formal controlled trial.

4 Trial Setting

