9.1 Sample Size

With a sample size of N=15 patients we should be able to detect changes of around the same order of magnitude as the variability in those differences (delta/sigma=1) with greater than 90% power on a one-sided test at the 5% level of statistical significance.

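### The exploratory MRI fat fraction is a count of fat-dominant voxels, insensitive to change below 50% fat, and muscle groups are examined only after a null global result

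*Protocol*

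**What the plan says.** Exploratory objective (c) in section 2.2 is "To investigate changes in muscle quality through the measurement of the global fat fraction of the upper and lower leg muscle compartments". The matching endpoint in section 2.4 is "Percentage change in fat fraction of upper and lower leg muscle compartments at baseline, 1 month and 6 months".

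Section 7.3.2 gives the operational definition. The images come from a fat-water separation method: "A custom 3-point Dixon sequence will be used to automatically segment the signals from skeletal muscle, bone and subcutaneous fat". The fat fraction is then found "by measuring the percentage of voxels in which fat predominates (>50% of the voxel) for the same defined anatomic region". Among the purposes of imaging, the same section lists the centre's methods "as well as conventional images to measure structure and muscle fat infiltration".

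On muscle groups, section 2.4 says: "If no difference is observed in this global measure, percentage changes in specific muscle groups (such as quadriceps and hamstrings) may also be measured". The table in section 2.5 repeats the condition: "analyses of muscle groups may also be performed if no change in global fat fraction is observed". Section 9.2 sets out tests for two muscle volumes and the creatine/water ratio. Its Bonferroni step concerns time points, and it does not mention fat fraction or muscle groups.

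**The concern.** There are two problems, and the first feeds the second.

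The name and the calculation do not match. A fat fraction is ordinarily read as the proportion of tissue that is fat. The quantity defined is how common fat-dominant voxels are. A voxel going from 5% to 45% fat counts as no change, while one going from 49% to 51% counts in full. To decide whether a voxel exceeds 50%, the software must already hold a fat estimate for it, so the dichotomy discards information the scan has supplied.

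The muscle-group step opens only when the global measure shows nothing. An insensitive global measure makes that more likely, and the search then continues in groups given only as examples. After a positive global result no such search is foreseen.

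Section 3 says the data will be used to power a controlled trial. A null on this measure could be misread as no change in muscle fat, and a positive in one muscle group could be carried forward without allowance for how it was found.

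**Working it through.** **The plan's own figure.** The only power statement is in section 9.1: "With a sample size of N=15 patients", delta/sigma = 1, one-sided 5%, power above 90%. With noncentrality √15 = 3.873 and 14 degrees of freedom, the paired t-test has power 97.9%; the normal approximation gives Φ(3.873 − 1.645) = 98.7%. The statement reproduces. It is generic and says nothing specific about fat fraction.

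**Inputs for the threshold.** The 50% cut comes from section 7.3.2. The documents give no voxel fat distribution and no expected change. Assumed: beta-distributed voxel fat with mean m = 5% to 20% and SD s = 3 to 15 points, and a uniform rise of 2 points in every voxel.

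**Formula.** k = m(1 − m)/s² − 1, a = mk, b = (1 − m)k. The count is P(X > 0.50) before the rise and P(X > 0.48) after it. The mean moves by exactly 2.0 points.

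**Example.** m = 0.10 and s = 0.10 give k = 0.09/0.01 − 1 = 8, a = 0.8, b = 7.2. The count goes from 0.438% to 0.584%, a change of 0.147 points, or 0.147/2 = 7% of the true rise.

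| Voxel SD (points) | Change in count, over means 5% to 20% (points) | Share of the 2-point rise |
|---|---|---|
| 3 | essentially 0 | essentially 0% |
| 5 | at most 0.0005 | below 0.03% |
| 8 | 0.03 to 0.08 | 2% to 4% |
| 10 | 0.15 to 0.32 | 7% to 16% |
| 15 | 0.21 to 0.97 | 11% to 49% |

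**Mixed tissue.** Suppose 5% of voxels are frank fat (mean 80%, SD 10) and the other 95% are muscle at mean 6% (SD 3). A 2-point rise in the muscle voxels moves the mean from 0.95×6 + 0.05×80 = 9.7% to 0.95×8 + 0.05×80 = 11.6%. The count stays at 4.97%.

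**Scale.** Fat fraction is itself a percentage, so a percentage change can be read as relative or in points. At m = 5% and s = 8 points, the count goes from 0.222% to 0.288%. That is 0.066 points, or 0.066/0.222 = 30% in relative terms. The two readings look very different.

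**Conditional muscle groups.** Assumed: 15 patients, no true change, the global measure taken as the average of the groups, paired t-tests at two-sided 5%, no adjustment, and correlation between groups from 0.8 down to 0. By simulation, the chance of at least one false positive across the global test and the groups is:

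- 2 groups: about 8% to 12%
- 4 groups: about 12% to 21%
- 6 groups: about 15% to 29%

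The global test alone gives 5%. The protocol names two groups, as examples; four and six are included only to show the range.

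**The case against.** The definition is openly stated and reproducible, and a count of fat-dominant voxels is a legitimate measure of frank fat, such as fat between muscles. It responds well when voxel fat is heterogeneous. If the mean doubles from 6% to 12% at a fixed beta concentration (a + b), the count goes from 0.0004% to 0.010% at concentration 20, but from 0.62% to 2.12% at 5 and from 2.8% to 6.6% at 2. In the last case it captures (6.6 − 2.8)/6 = 63% of the rise. This stands: the loss depends on a distribution the documents do not give. The comparison in points is also not a power calculation, because the repeatability of neither measure is stated.

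A reader might infer that the measure is blind to the very change it targets, diffuse fat. The documents support neither half of that. They speak of infiltration and muscle quality, never of diffuse change, and voxels crossing 50% are seen.

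A reader might also multiply out 1 − 0.95³ = 14.3% for the global test plus two groups. That assumes independence, which cannot hold because the global measure contains the groups.

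Finally, the muscle-group step is optional and exploratory, no significance test is specified for it, and error control may lie in an analysis plan not shown. That tempers the second problem. It does not remove the asymmetry, which the protocol itself fixes.

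**Conclusion.** The point holds as a limited one. The quantity called fat fraction is a prevalence of fat-dominant voxels. Under the assumed distributions it loses from about half (51% at voxel SD 15 points, mean 20%) to essentially all (SD 5 points or less) of a uniform 2-point rise. A change that also widens the voxel distribution is captured better.

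The null-triggered muscle-group step would raise the chance of any false positive from 5% to about 8% to 12% for two groups, if they were tested unadjusted at 5%.

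The effect is confined to exploratory endpoint (c). It would be too strong to call that endpoint uninterpretable: the count can be read for what it is, provided it is named so. The primary muscle-volume endpoint and the sample size are unaffected. The change is still worth making, because the better measure comes from images already planned.

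**What to change.** In sections 7.3.2, 2.4(c) and 2.5:

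- Define fat fraction as the mean over the muscle compartment of the voxelwise Dixon percentage, fat/(fat + water), and analyse it as absolute change in percentage points.
- Keep the over-50% count as a descriptor under its own name, percentage of fat-dominant voxels.
- Name any muscle groups in advance and report them whatever the global result, or drop them.

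The first two changes are wording and a different summary of the same images, with no extra scanning. The third costs a little analyst time to delineate muscle groups if they are kept.

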9.1 Sample Size

With a sample size of N=15 patients we should be able to detect changes of around the same order of magnitude as the variability in those differences (delta/sigma=1) with greater than 90% power on a one-sided test at the 5% level of statistical significance.

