2.1 Primary objective

a. To identify a change in muscle bulk when RA patients with active inflammation are treated with Tofacitinib.

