6.8 Withdrawal criteria

Participants may withdraw from the study at any point without the requirement for any further involvement. If a participant wishes to withdraw from certain aspects of follow-up (e.g. repeat muscle biopsy) but to continue with other study assessments, this will be

permitted and encouraged. The PI may also withdraw patients from the study for medical reasons.

Participants who fail screening will be replaced but participants who drop out after the baseline visit will not be replaced. Where there is appropriate consent, their data will be used within the study report.

Participants who discontinue tofacitinib after visit 4, for whatever reason, will be invited to attend for an early withdrawal visit at the earliest opportunity. Participants will be encouraged to undergo the full range of study assessments if willing to do so but, if a participant wishes to decline some procedures but undergo others, this will be permitted and encouraged. Participants may also decline an early withdrawal visit in toto. At the discretion of the PI, aspects of the early withdrawal visit may be omitted depending on the time interval since they were last performed.

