9.2 Primary Endpoint Analysis

The MRI studies will provide continuous data for the muscle volume (in cm³) of both legs. There will be two volume measurements, one for the lower leg and one for the upper legs at the three timepoints. There will be one spectroscopic measurement which is the ratio of creatine to water in the soleus for all three time points. There are therefore three outcome measures at three time points for each of 15 individuals.

Each outcome measure will be tested for suitability for a one-way repeated ANOVA assessment (checks for outliers, normality, homogeneity and sphericity). If the ANOVA is significant, post-hoc testing will be carried out using Bonferroni correction to identify which timepoints are significantly different. Effect sizes will be calculated.

In the event that the data do not satisfy the criteria for one-way repeated ANOVA, then Friedman's ANOVA will be performed, followed by step-wise post-hoc tests to identify which timepoints are significantly different. Effect sizes will be calculated. All statistics will be performed using IBM SPSS Statistics 24.

Should we establish significant changes in both muscle volume and creatine/water ratio, then we will further investigate the relationship between these changes, bearing in mind the size of this pilot study.

10 Ethics & Regulatory Issues

The conduct of this trial will be in accordance with the ethical principles for medical research involving human subjects determined by the World Medical Association Declaration of Helsinki of the 64th General Assembly in October 2013. All members of the research team and the investigators will be trained in the statutory instrument and those aspects of Good Clinical Practice appropriate to their role in the trial. Favourable ethical opinion and Clinical Trial Authorisation from relevant Competent Authority(ies) will be sought prior to commencement of the trial. Local approvals will be sought before recruitment may commence at each site. Information sheets will be provided to all eligible subjects and written informed consent obtained prior to any trial procedures

11 Confidentiality

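### The power in section 9.1 is for a single one-sided test, not for the ANOVA with Bonferroni comparisons planned in section 9.2

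*Protocol*

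**What the plan says.** Protocol section 9.1 sets 15 patients against an effect as large as the spread of the within-patient differences. Its power statement reads: "delta/sigma=1) with greater than 90% power on a one-sided test at the 5% level of statistical significance".

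Section 9.2 plans something else: "Each outcome measure will be tested for suitability for a one-way repeated ANOVA assessment". Where that test is positive, a second step follows: "If the ANOVA is significant, post-hoc testing will be carried out using Bonferroni correction to identify which timepoints are significantly different". The fallback is Friedman's ANOVA with step-wise post-hoc tests. Section 9.2 gives neither the sidedness of the post-hoc tests nor the number of comparisons corrected for.

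The primary objective (section 2.1) has no direction: "To identify a change in muscle bulk when RA patients with active inflammation are treated with Tofacitinib". Section 2.3 defines the primary endpoint over baseline, 1 month and 6 months without ranking the time points. On losses, section 6.8 says that "participants who drop out after the baseline visit will not be replaced"; no drop-out rate is given.

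**The concern.** The power statement and the primary analysis stand next to each other in the same protocol and refer to different tests. Neither the ANOVA F test nor Friedman's test has a direction, and a Bonferroni-corrected comparison uses a stricter threshold than a single one-sided 5% test. A reader would take the figure of more than 90% as the power to show that muscle volume at 6 months differs from baseline. Under the planned post-hoc step, that power is lower.

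The study is meant to supply data for powering a controlled trial. A non-significant pairwise result would be read against a claimed miss rate below 10%, when the miss rate at the stated effect is about 14% with all 15 patients and three corrected pairs. It rises with every patient lost.

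**Working it through.** **Inputs.** From section 9.1: n=15, delta/sigma=1 with sigma the SD of the within-patient differences, one-sided alpha 0.05. From section 9.2: three time points, hence 3 possible pairs and alpha 0.05/3 = 0.0167 per pair. Two-sidedness and the count of three are inferred. Completer numbers below 15 are assumptions.

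**Pairwise formula.** Paired t-test, df = n-1, noncentrality = (delta/sigma) × √n, power from the noncentral t distribution. For n=15 the noncentrality is √15 = 3.873.

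**1. The protocol's own figure.** One-sided 5%, n=15, critical t(14) = 1.761: power 97.9%. The claim of more than 90% is correct for this test, and holds even with 12 patients (94.5%).

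**2. Pairwise comparisons at delta/sigma=1, n=15.**

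| Test | Critical t | Power |
|---|---|---|
| One-sided 0.05, single | 1.761 | 97.9% |
| Two-sided 0.05, single | 2.145 | 94.9% |
| Two-sided 0.05/2 (two comparisons with baseline) | 2.510 | 89.8% |
| Two-sided 0.05/3 (all three pairs) | 2.718 | 85.8% |
| One-sided 0.05/3 | 2.360 | 92.2% |

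Requiring a significant omnibus F first changes little: simulation (100,000 replicates, compound symmetry, SD of differences 1) gives 85.0-85.7% for the three-pair test, depending on the 1-month mean.

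**3. Omnibus ANOVA, n=15.** Under compound symmetry with SD of differences 1, the within-patient error variance is 0.5. The noncentrality is n × Σ(mean − grand mean)² / 0.5, with F on 2 and 28 df and critical value 3.340.

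- 1-month mean halfway, profile (0, 0.5, 1): Σ = 0.5, noncentrality 15, power 91.7%.
- 1-month mean equal to baseline or to 6 months, profile (0, 0, 1) or (0, 1, 1): Σ = 2/3, noncentrality 20, power 97.4%.

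**4. Fewer completers (assumed), delta/sigma=1.**

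| Completers | Two-sided 0.05/3 | Two-sided 0.05/2 | Single two-sided 0.05 |
|---|---|---|---|
| 15 | 85.8% | 89.8% | 94.9% |
| 14 | 82.3% | 87.0% | 93.2% |
| 13 | 78.0% | 83.5% | 91.1% |
| 12 | 73.0% | 79.3% | 88.3% |

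Omnibus power with 12 completers is 83-93% (noncentrality 12 to 16, F on 2 and 22 df).

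**5. Effect detectable at 90% power, n=15.** 0.80 SD for the one-sided single test and 1.06 SD for the two-sided three-pair test. At delta/sigma=1 the three-pair test needs 17 evaluable patients for 90% (91.1%).

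**The case against.** The strongest defence is that the first-line test in section 9.2 is the omnibus ANOVA, and that it exceeds 90% at the stated effect with 15 patients. For an objective of finding any change, that is arguably the relevant test. This stands, and it rules out the stronger reading that the planned analysis as a whole is underpowered. The shortfall concerns the step that says which time points differ, and the case of fewer completers.

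Second, three two-sided pairs is an inference. Section 7.3.2 speaks of comparing baseline with the 1-month and 6-month measurements, which suggests two comparisons (89.8%). The hypothesis in section 1.3 is directional, and one-sided tests over three pairs would give 92.2%. This also stands, so 86% is one plausible reading and not the only one. With one patient lost, however, even those readings fall to 87.0% and 89.9%.

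Third, the protocol gives no drop-out rate, so 12 completers is purely an assumption. Stopping tofacitinib also need not mean losing the late scan: section 6.8 offers an early withdrawal visit, and the schedule in section 6.1 allows repeat MRI there if at least 3 weeks have passed since the original imaging.

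Fourth, section 5.1 says that the sample size was set by feasibility, and section 9.2 calls the study a pilot. That lowers the weight of the point but does not make the power statement describe the planned analysis.

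A reader might also infer that section 9.1 contains a calculation error, or that 6 months must be the sole primary comparison. The documents support neither: the figure is right for the test it names, and section 2.3 does not rank the time points.

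**Conclusion.** Sections 9.1 and 9.2 are inconsistent. The stated power belongs to a one-sided single comparison that section 9.2 does not plan.

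For the planned analysis at delta/sigma=1 with 15 complete patients, the claim of more than 90% holds for the omnibus test. It does not hold for a two-sided Bonferroni-corrected pairwise comparison, although with only two comparisons the shortfall is marginal. Pairwise power drops further with each loss.

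The omnibus figures assume sphericity and depend on the 1-month mean. The pairwise figures depend on the inferred sidedness and number of comparisons. All figures are per outcome measure. Severity is moderate to minor: the wording of a quantitative claim needs correcting, and the sample size itself rests on feasibility.

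**What to change.** Restate section 9.1 as the power of the analysis in section 9.2. Give the omnibus and pairwise figures separately, and state two-sided testing, the number of comparisons corrected for and the assumed number of completers. An example for three pairs: with 15 evaluable patients, about 86% power for a pairwise change of 1 SD, or 90% power for 1.06 SD; with 12 evaluable, 73% at 1 SD. State the sidedness and number of comparisons in section 9.2 as well. This costs a few sentences and no extra patients; the stated figure becomes less favourable.

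Optionally, if the sponsor regards 6 months as the main time point, pre-specify one two-sided 5% contrast from baseline to 6 months per outcome, and test 1 month only if that contrast is significant. Power at 1 SD is then 94.9% with 15 completers, 91.1% with 13 and 88.3% with 12. This is a design choice rather than a correction, and its price is that the 1-month comparison becomes conditional.
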